17.2 Determination of Sample Size

The sample size for this study is not based on a formal statistical calculation. In total, approximately 300 subjects who have successfully completed Study MT-1186-A02 will be enrolled in this study. However, data from 380 subjects (190 subjects per group) randomized in Study MT-1186-A02 will be included for all analysis. Using Study MT-1186-A02 and MT-1186-A04 survival data, the planned sample size of 190 subjects per group initially randomized in Study MT-1186-A02 will have 70% power to detect a statistically significant result if the true hazard ratio between edaravone 105 mg daily (test) and edaravone 105 mg on/off regimen (control) in the primary endpoint is 0.775, which means 22.5% risk reduction in the hazard due to daily treatment, assuming 65% survival rate at Week 48 for the control group. This calculation of 70% power assumes a 2-sided alpha of 20% based on a rare disease condition, 19 using the log-rank test and a follow-up time of up to 48 weeks in Study MT-1186-A04.

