4.2. Sample Size and Power Considerations

In total, approximately 300 subjects who have successfully completed Study MT-1186-A02 are anticipated to be enrolled in this MT-1186-A04 study. A formal sample size calculation was not performed. However, data from 380 subjects (190 subjects per group) randomized in Study MT-1186-A02 will be included for all analyses. Hence, using MT-1186-A02 and MT-1186-A04 survival data and assuming 65% survival rate of the primary endpoint for the control group, the planned sample size of 190 subjects per group initially randomized in Study MT-1186-A02 will provide 70% power to detect a statistically significant result if the true hazard ratio between edaravone 105 mg daily (test) and edaravone 105 mg on/off regimen (control) in the primary endpoint is HR=0.775 (implying 22.5% risk reduction in the hazard due to daily treatment). This calculation of 70% power assumes a 2-sided alpha of 20% based on a rare disease condition (Hilgers RD et al., 201614) using the log-rank test and a follow-up time of up to 48 weeks in Study MT-1186-A04.

When this SAP version 1.0 was finalized and signed, for 384 subjects randomized in Study MT-1186-A02, 202 subjects who have successfully completed Study MT-1186-A02 were enrolled in this MT-1186-A04 study.

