6.1.2. Efficacy Full Analysis Set (FAS)

The full analysis set (FAS) is defined as all of the subjects randomized in Study MT-1186-A02 who received at least 1 dose of study medication in Study MT-1186-A02. Subjects in the FAS will be grouped and analyzed based on the planned treatment allocated (as randomized). Efficacy endpoints will be analyzed using the FAS.

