Since the MT-1186-A02 and MT-1186-A04 clinical trials will not collect information on King's Stage directly, ALSFRS-R item responses and patients' survival will be mapped to stages for every ALSFRS-R collected visit using the above published algorithm and patientlevel data. Patients with baseline ALSFRS-R assessments at MT-1186-A02 that will not meet criteria for lower limb, upper limb, or bulbar involvement, and that also will not have evidence of Stage 4A or Stage 4B, will be designated "Stage 0", as their assessments could not be mapped to the King's ALS Clinical Staging System. For the King's stage derivation, the available ALSFRS-R data at each analysis visit will be used in the subjects who were not dead. If the subject was reported as death from the last observation visit to last day of the nearest analysis visit window, the King's stage from the analysis visit will be Stage 5. If a subject not reported as death will have missing ALSFRS-R assessment at each visit, the last observation will be carried forward for the last King's stage value: In the vast majority of circumstances patients will either remain in the same clinical stage from one assessment to the next or they will experience a decline in stage. In those relatively rare instances, in which subject will be found to improve from one assessment to the next, the value from their immediately prior assessment will be used rather than the actual observed value, because the improvement will be considered to be temporary or spurious.

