9.2.2.2.3. King's ALS Clinical Stage Derived from ALSFRS-R Score and Death Event

King's ALS Clinical Stage analysis will be done using the FAS. A shift table to each visit throughout the periods of both MT-1186-A02 and MT-1186-A04 from baseline category will be summarized using number and percentages.

Mitsubishi Tanabe Pharma America, Inc.

For the Kings ALS Clinical Staging System, attention will focus on two events of clinical progression:

- Any decline in stage from baseline
- Any \geq 2-stage decline from baseline

These events will be analyzed in terms of both the proportion of patients who will experience the events between baseline and visit Week 96 (A04 Week 48) in MT-1186-A04 using chi square test for proportions, as well as the time to these events using stratified log rank test using the randomization strata of ALSFRS-R rate of decline score during the screening period (2 levels strata of -1,-2 or -3,-4), Geographical Region (3 levels strata of Europe, America or Asia Pacific). For the latter, study dropouts prior to any event will be treated as censored as of the date of their first missing assessment. The time to event will be also displayed using the Kaplan Meier figure. Comparisons will be made between treatment groups on an overall basis, as well as controlling for King's stage at baseline using Cochran–Mantel–Haenszel test (CMH).

Mitsubishi Tanabe Pharma America, Inc.

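### King's stage to Week 96: 47% of randomised subjects had not entered A04, and those still event-free are shown at their last stage and counted as non-progressors

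*SAP*

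**What the plan says.** - **Analysis set.** SAP 9.2.2.2.3: "King's ALS Clinical Stage analysis will be done using the FAS". Under SAP 6.1.2 a subject is in the FAS once randomised and dosed in A02. Entry to A04 plays no part.
- **Missing stage.** SAP 8.3.2.3: if a subject not reported dead has no ALSFRS-R at a visit, "the last observation will be carried forward for the last King's stage value". The same section expects patients to hold or worsen in stage in nearly all cases, and overrides an observed improvement with the preceding value.
- **Death.** SAP 8.3.2.3 assigns Stage 5: "If the subject was reported as death from the last observation visit to last day of the nearest analysis visit window" is the condition that triggers it.
- **Outputs.** SAP 9.2.2.2.3 plans shift tables from baseline to each visit across both studies. It defines two events, any decline and a decline of two or more stages. The proportion with each event from baseline to Week 96 is compared "using chi square test for proportions". The time to each event is compared by stratified log-rank test with a Kaplan-Meier figure, and there dropouts without an event are censored at their first missing assessment.
- **Follow-up.** SAP 4.2: "for 384 subjects randomized in Study MT-1186-A02, 202 subjects who have successfully completed Study MT-1186-A02 were enrolled in this MT-1186-A04 study". Protocol 17.2 had expected more: "In total, approximately 300 subjects who have successfully completed Study MT-1186-A02 will be enrolled in this study". SAP 5.1 and 5.2 record that A04 was stopped and that only the interim analysis, on data up to the A02 cessation, will be done.
- **Status.** SAP 3.3.3 lists King's stage as exploratory, and SAP 9.2.2.2 makes no overall Type I error correction.

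**The concern.** There are two separate problems, and they need separate remedies.

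**(a) Shift tables.** Carry-forward assumes no change after the last assessment. Because the SAP expects stages to hold or worsen, and discards improvements, the error runs one way: progression can be missed but not overstated. The later the visit, the more of the table is carried forward. The convention also differs from the ALSFRS-R model (no imputation, SAP 9.2.2.1.2) and from CAFS (multiple imputation, SAP 8.3.2.2). Protocol 17.4.2.2 rules out imputing from outside the visit window. The SAP may override the protocol, but its section 11 lists only the FAS change.

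**(b) Chi-square test.** The Week 96 proportion is cumulative. A FAS subject who was event-free when last seen, at Week 24 or Week 48 for example, enters the denominator as a non-progressor to Week 96. The log-rank test in the same paragraph treats such a dropout as censored, so the plan gives one subject two different statuses for the same event.

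At stake are the level of the reported proportions, which will be too low, and the comparison between arms if follow-up differs: the arm with less follow-up would look better.

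**Working it through.** The documents give no planned rate or power figure for King's stage. The only stated power is 70% for the primary endpoint. It reproduces with exponential survival and 96 weeks of follow-up, and its rates serve as a stand-in in step 4:
- control event-free at 96 weeks 0.65² = 0.4225; daily 0.4225^0.775 = 0.513
- expected events 190 × (0.5775 + 0.4871) = 202.3
- power = Φ(√202.3 × |ln 0.775| / 2 − 1.282) = 70.2%

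**Step 1. Subjects with no A04 data.** 384 − 202 = 182, and 182/384 = 47.4%. The plan implied (380 − 300)/380 = 21.1%. The FAS count is not given, so 384 stands in for it.

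**Step 2. Entrants cut short.** The number reaching Week 96 is not given. If a share r of the 202 reached it, 1 − 202r/384 have no observed Week 96 assessment (this includes deaths):

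| r (assumed) | No Week 96 assessment |
|---|---|
| 100% | 47.4% |
| 75% | 60.5% |
| 50% | 73.7% |
| 25% | 86.8% |

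**Step 3. Who is frozen as a non-progressor.** Non-entrants who had already declined or died count as events. With q the share already counted (not given, so assumed), the frozen share of the denominator is 182(1 − q)/384:

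| q (assumed) | Subjects | Share of denominator |
|---|---|---|
| 0% | 182 | 47.4% |
| 20% | 146 | 37.9% |
| 35% | 118 | 30.8% |
| 50% | 91 | 23.7% |
| 80% | 36 | 9.5% |

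For the two-stage event q is smaller than for any decline, so more subjects are frozen.

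**Step 4. Effect on the proportions.** Assume every non-entrant was last seen at Week 48. The crude proportion is then (202/384) × p96 + (182/384) × p48.
- p48 = 35%, p96 = 60%: 31.6% + 16.6% = 48% instead of 60%.
- p48 = 45%, p96 = 70%: 36.8% + 21.3% = 58% instead of 70%.
- Primary-endpoint rates with HR 0.775: 57.75% v 48.71% (difference 9.0 points) becomes 46.97% v 39.08% (7.9 points). Chi-square power at two-sided 5% with 192 per arm falls from 42.6% to 34.5%.

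**Step 5. Unequal entry, no treatment effect.** The artefact is (difference in entry) × (p96 − p48).
- Exponential with a 60-week median (assumed): p48 = 1 − 2^(−0.8) = 42.6%, p96 = 1 − 2^(−1.6) = 67.0%. Entry of 47.5% v 57.5% (assumed) gives 54.2% v 56.6%, a gap of 2.4 points.
- Primary-endpoint control rates: 0.10 × 22.75 = 2.3 points; a 20-point difference in entry gives 4.6 points.
- For scale, the standard error of a difference near 55% with 192 per arm is √(2 × 0.554 × 0.446 / 192) = 5.1 points, so 2.4 points is about half a standard error.

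**The case against.** Four stronger readings are tempting, and the documents support none of them.

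- **That about half the denominator is counted as unable to progress.** 47.4% is the share that had not entered A04. Non-entrants with a recorded decline are already events, and reported deaths become Stage 5. For non-entrants, 47.4% is only the ceiling.
- **That carry-forward biases the chi-square test.** The tested quantity is whether the event ever occurred. Repeating the last stage neither adds nor removes an observed decline, so with the whole FAS as denominator the numerator is the same either way. The fault in the test is a crude cumulative proportion under unequal follow-up. Carry-forward matters mainly for the shift tables.
- **That a spurious treatment difference is to be expected.** The documents give no A04 entry by arm. The 10-point imbalance is an assumption, and the resulting gap is small against its standard error.
- **That the proportion is the only analysis.** A censored, stratified log-rank test of the same events is already planned.

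These objections limit the size of the point and separate its two parts. They do not answer either part: the shift tables still present unobserved stages as observed, and the chi-square test still treats absence of follow-up as absence of progression.

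Two uncertainties remain. Some non-entrants left A02 early and would be frozen from before Week 48. The Stage 5 rule refers only to the nearest visit window, so it is unclear whether a later death of a non-entrant counts.

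**Conclusion.** The point holds as a modest correction to an exploratory analysis. It rests on the FAS definition, the carry-forward rule, the chi-square test up to Week 96, and the entry of 202 of 384 subjects, all of which are in the SAP. Among non-entrants, 38% to 24% of the denominator is alive, event-free and frozen if 20% to 50% had already declined (assumed), with 47% as the upper bound. Entrants cut short by the termination add to this by an amount that the documents do not allow to be calculated.

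The main consequence is a Week 96 proportion that is too low, by about 12 points in the two illustrative cases of step 4. A false difference between arms is possible but would be about 2.4 points for a 10-point difference in entry, and nothing in the documents shows such a difference. The primary and secondary endpoints are not touched.

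**What to change.** 1. **Shift tables (SAP 8.3.2.3 and 9.2.2.2.3).** Drop carry-forward. Show the observed stage at each visit, Stage 5 for reported deaths, and a 'missing' row, by arm. State whether deaths after the nearest visit window count as Stage 5 at later visits.
2. **Week 96 comparison (SAP 9.2.2.2.3).** Replace the chi-square test, for both events, with the between-arm difference in Kaplan-Meier estimates and its confidence interval. Take it at Week 96, or at the latest week with adequate numbers at risk, and write the threshold for adequate into the SAP beforehand. The estimates come from the time-to-event analysis already planned. Say explicitly that non-entrants and entrants cut off by the termination are censored in the same way as other dropouts. If the Cochran-Mantel-Haenszel comparison is meant for the same proportion, it needs the same change.
3. **State the assumption.** Kaplan-Meier estimation assumes non-informative censoring. If sicker subjects were less likely to enter A04, it too would understate progression. Report A04 entry and last assessment time by arm so that the reader can judge.

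A missing row alone would leave the chi-square test unchanged, so items 1 and 2 are both needed. The cost is SAP wording and revised table shells, with no new data. Intervals at late visits will be wider.

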8.3.3. Safety Measures

8.3.3.1. Adverse Events

An AE is any untoward medical occurrence in a subject or clinical investigation subject administered a pharmaceutical product that does not necessarily have a causal relationship with this IMP. An AE can therefore be any unfavorable and unintended sign (including an abnormal laboratory finding, for example), symptom, or disease temporally associated with the use of an IMP, whether or not considered related to the IMP.

Adverse events will be coded according to the MedDRA version 23.0

- Adverse Events will be classified for Treatment Emergent AEs (TEAEs) if at least one of the following conditions is met:
 - The AE was not present before the first dose in Study MT-1186-A02 but started after administration of the first dose of study drug in Study MT-1186-A02, or,
 - The AE was present before the first dose in Study MT-1186-A02 but increased in severity following administration of the first dose of study drug in Study MT-1186-A02.

Mitsubishi Tanabe Pharma America, Inc.

Integration of continued AEs from MT-1186-A02 to MT-1186-A04:

TEAE's from MT-1186-A02 will be integrated into TEAE's from the current MT-1186-A04 study in order to be able to analyze the continued safety profile. If AE in MT-1186-A04 met all following conditions, the AE in MT-1186-A02 and MT-1186-A04 will be merged into a single AE.

- Onset date of AE in MT-1186-A02 = Onset date of AE in MT-1186-A04
- Lowest level terms (LLT) of AE in MT-1186-A02 = LLT of AE in MT-1186-A04
- "Was this event ongoing at the end of MT-1186-A02?" in MT-1186-A04 CRF = "Yes" Then, for AE analysis, AE End date and Outcome data in MT-1186-A04 CRF data rather than MT-1186-A02 CRF data will be prioritized and analyzed.

Handling Partial Dates:

The handling of partial dates in study MT-1186-A02 were provided in a designated SAP for this study. The following are the rules for partial dates handling for TEAE's newly captured in MT-1186-A04 study:

- AE with a missing start time, but with a start date equal to the date of first dose of study treatment in MT-1186-A04 will be considered treatment-emergent.
- If the AE start date is incomplete, it will be imputed as follows for the purpose of determining TEAE:
 - o If the start date is completely missing, the start date will be equal to the date of the first dose date of study drug in MT-1186-A04. However, if the stop date is not missing and is before the date of the first dose of study drug in MT-1186-A02, then the stop date will be used instead, and the AE will not be considered as TEAE.
 - o If the start day is missing, but the month and year are not missing and are equal to the month and year of the first study dose in MT-1186-A02, then this event will be considered as TEAE.
 - o If the start day and month are missing, then the first day of the first month (January) will be used.
- If an AE stop date is incomplete, it will be imputed as follows for the purpose of determining AE duration:
 - o If the AE stop date is completely missing, then the stop date will be equal to the subject's last observed date in MT-1186-A04.
 - If the Stop day is missing, but the month and year are not missing and are equal to the month and year of the last observed date in MT-1186-A04, then stop date will be equal to last observed date.

Mitsubishi Tanabe Pharma America, Inc.

- o If the start day and month are missing, then the first day of the first month (January) will be used.
- Adverse Events will be classified for Adverse Drug Reactions (ADR) if an AE is valuated as having causally related to the investigational product with "a reasonable possibility"

Serious Adverse Events

A serious Adverse Event (SAE) is defined as any untoward medical occurrence that at any dose:

- Results in death;
- Is life-threatening;
- Requires hospitalization or prolongation of existing hospitalization;
- Results in persistent or significant disability or incapacity;
- Is a congenital anomaly or birth defect;
- Is an important medical event.

All SAEs occurring from the time written ICF is obtained from a subject until the end of the Safety Follow-up period or the withdrawal of the subject from the study must be reported to the Sponsor/CRO. All SAEs and AESI must also be entered in the AE section of the eCRF within 24 hours.

Duration of Adverse Events

After the integration of TEAEs from MT-1186-A02 into TEAEs from MT-1186-A04, the following rules will be applied to calculate duration of TEAE's:

Duration of the AE and time to the AE occurrence from start of study drug in MT-1186-A02 will be calculated and presented in days

- Duration = AE stop date AE start date + 1
- Time to AE occurrence = AE start date The first administration date of study drug in MT-1186-A02 + 1.

Definition of Oral subgroup and PEG subgroup

Subjects are starting with oral administration while opting to switch from oral administration to PEG/RIG dosing based the patient's disease progresses. Therefore, if subject switched from oral dosing to PEG/RIG then the subject will be classified to the PEG subgroup. Otherwise, the subjects will be classified as Oral subgroup.

Mitsubishi Tanabe Pharma America, Inc.

Definition of TEAE under Oral dosing and PEG dosing

If the subjects have the date subject switched to PEG/RIG dosing, TEAEs after the switched date will be defined as TEAEs under PEG dosing. Otherwise TEAEs will be defined as TEAEs under Oral dosing.

- If switch date is incomplete, it will be imputed as follows for the purpose of determining PEG duration:
 - o If the switch day is missing, but the month and year are not missing, then the 15th will be used.

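### SAP 8.3.3.1 sets a year-only AE start to 1 January with no floor at the A02 first dose, so a few on-treatment AEs lose TEAE status, and a fully missing start can be imputed after a known stop

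*SAP*

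**What the plan says.** SAP 8.3.3.1 leaves A02 partial dates to the A02 plan and then sets its own scope: "The following are the rules for partial dates handling for TEAE's newly captured in MT-1186-A04 study". The first limb of the TEAE definition in the same section uses the A02 first dose: "The AE was not present before the first dose in Study MT-1186-A02 but started after administration of the first dose of study drug". The other limb, worsening after first dose, uses the same reference.

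Start-date imputation has a stated purpose: "If the AE start date is incomplete, it will be imputed as follows for the purpose of determining TEAE". Three rules follow.

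- **Start completely missing.** The start is set to the first dose in A04. The exception applies only "if the stop date is not missing and is before the date of the first dose of study drug in MT-1186-A02"; the stop date then replaces the start and the AE is not a TEAE.
- **Day missing.** The AE is a TEAE if "the month and year are not missing and are equal to the month and year of the first study dose in MT-1186-A02".
- **Day and month missing.** "If the start day and month are missing, then the first day of the first month (January) will be used". No lower bound is given, and there is no check against the stop date.

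SAP 8.3.1.4 treats another date differently. A PEG/RIG switch date imputed to before the first study drug is moved up to the date of that first dose.

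**The concern.** Imputing a start date to decide treatment emergence should not make a more complete record count less than an empty one. Here it can. An AE with no start date is placed at the A04 first dose and is a TEAE. If the site also records the year, and that is the year of the A02 first dose, the same AE moves to 1 January, before treatment began, and is not a TEAE. It then drops out of every TEAE table in SAP 9.3.1.

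The completely-missing rule has a different flaw. It imputes from one reference date (A04 first dose) and tests its exception against another (A02 first dose). A stop date between the two is caught by neither, and the imputed start falls after the known stop.

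Safety and tolerability is the secondary objective. SAP 5.1 and 5.2 say that the interim analysis on all accumulated data goes ahead and the final analysis does not, so these rules will be applied once, in the only planned A04 safety readout.

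**Working it through.** The plan states no figure here. The check applies the written rules to every possible first-dose date.

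**Inputs**
- A04 Day 1 is the A02 Week 48 visit (SAP 4.1, Figure 1 notes), nominally Day 337, with an analysis window of Day 295 to 379 (SAP 8.4). At nominal timing the offset from A02 first dose to A04 Day 1 is 336 days.
- TEAE reference date: A02 first dose (SAP 8.3.3.1).
- Assumptions: A02 first dose uniform over a 365-day year; onset uniform from A04 Day 1 to 350 days later (351 days: 48 weeks plus the 2-week follow-up).

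**1. Year-only start, onset in A04**

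Number the days of the year from 1 January = 1, and let the A02 first dose fall on day d. TEAE status is lost when 1 January precedes the dose (d ≥ 2) and the A04 onset is in the same calendar year (d + offset ≤ 365 at the earliest).

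- Affected first-dose dates: n = 365 − offset − 1. At 336 days, n = 28, which is 2 to 29 January.
- Each such date leaves between 28 and 1 onset days before year end, mean 14.5. Total = n(n + 1)/2 = 28 × 29/2 = 406.
- Share of onset days: 406/(365 × 351) = 0.32%. With 336 onset days instead of 351: 406/(365 × 336) = 0.33%.

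| A04 Day 1 falls on A02 day | Offset (days) | Affected dates of 365 | Share of onset days |
|---|---|---|---|
| 295 | 294 | 70 | 1.9% |
| 330 | 329 | 35 | 0.5% |
| 337 (nominal) | 336 | 28 | 0.3% |
| 344 | 343 | 21 | 0.2% |
| 379 | 378 | 0 | 0% |

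These are shares of onset days. The share of AEs affected is this figure times the proportion of AEs recorded with year only, which the documents do not give.

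Example: A02 first dose 10 January 2022, A04 Day 1 12 December 2022, true onset 20 December 2022, recorded as 2022. The imputed start is 1 January 2022, so the AE is not a TEAE. If the imputed date were also used for time to occurrence, the result would be −9 + 1 = −8 days.

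**2. Completely missing start, known stop**

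The start is set to A04 Day 1 unless the stop precedes the A02 first dose. At nominal timing, a stop on any of the 336 days from the A02 first dose to the day before A04 Day 1 gives a start after the stop.

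Example: A02 first dose 15 July 2021, A04 Day 1 16 June 2022, stop 1 June 2022. The imputed start is 16 June 2022 and the AE is a TEAE. Duration by the SAP formula (stop minus start plus 1) would be −15 + 1 = −14 days if the imputed date were used.

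**3. Day-missing start**

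The A02 first-dose month ends at most 30 days after that dose, and A04 begins 294 days or more after it within the analysis window. No A04 onset can match the month: 0 of 365 first-dose dates at each of the five offsets. An A04 onset with known month and year is after the A02 first dose whatever the day, so its status is not in doubt.

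**The case against.** The strongest reply is that most of what a reader might infer here does not follow from the documents.

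- **Using A02 as the reference is not an error.** It matches the TEAE definition. The day-missing clause addresses the only month in which status is ambiguous. For A04 onsets it is redundant, not wrong. This stands.
- **Dating an AE before A04 entry changes no TEAE table.** A year-only onset in the calendar year of A04 entry is dated before A04 Day 1 for almost every subject, which looks large. But SAP 9.3 summarises A02 and A04 data together, and emergence is judged from the A02 first dose. This stands.
- **Time to onset, duration and Oral/PEG attribution are conditional.** The SAP also says "TEAEs after the switched date will be defined as TEAEs under PEG dosing", so a reader might conclude that AEs under PEG/RIG will be counted as oral. That requires the imputed start to be used there, and the stated purpose is limited to determining TEAE status. The SAP does not say which start date those calculations use. This stands.
- **Few records qualify.** Protocol 15.6 asks for onset date and time, and Protocol 16.1 and 16.3 provide for queries. AEs are recorded from consent, so one that ended before A04 Day 1 would ordinarily sit in the A02 database. This limits the number but does not remove the fault: the SAP's own exception provides for A04-captured AEs that stopped even before the A02 first dose.
- **The uniform-onset assumption is rough**, because the study was terminated early. Shorter follow-up would raise the share somewhat: with onset limited to an assumed 168 days, 406/(365 × 168) = 0.7%.

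None of this answers the year-only rule. Its purpose is to determine TEAE status, and applied as written it can give the wrong status.

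**Conclusion.** The concern holds in a narrow form. The year-only rule has no floor at the TEAE reference date and can reclassify an on-treatment AE as not treatment-emergent. For onsets in A04 at nominal timing this needs an A02 first dose on 2 to 29 January, about 0.3% of onset days under the uniform assumptions (0% to 1.9% across the Week 48 analysis window), and a record with neither day nor month. An A02-period AE first entered in A04 as year-only would lose status in the same way if its year is that of the A02 first dose; how many such records exist is unknown. Few AEs are affected, and nothing in the documents suggests a material change to the safety conclusions.

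The completely-missing rule can put a start after a known stop. The AE stays a TEAE, which is the right default, and a negative duration arises only if the imputed date is carried forward.

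The documents do not support a broader claim that the rules misclassify A04 AEs generally, or that they bias time to onset or the Oral/PEG comparison.

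**What to change.** Amend the start-date rules in SAP 8.3.3.1:

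1. Keep the imputed start compatible with the recorded part, but not before the A02 first dose unless the recorded part or the stop date shows onset before that dose. For a year-only date, use the later of 1 January and the A02 first dose when both fall in the recorded year. SAP 8.3.1.4 already uses this kind of floor for the PEG/RIG switch date.
2. Classify the AE as a TEAE unless the recorded part or the stop date shows onset before the A02 first dose.
3. Never impute a start after a known stop date. For a completely missing start, use the earlier of the A04 first dose and the stop date.
4. State whether the imputed start is used for duration, time to occurrence and Oral/PEG attribution, or only for TEAE status.

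The cost is a few lines of SAP text and programming. The TEAE count may rise slightly, because a year-only AE that truly began in the first-dose year before dosing would be counted. That is the conservative direction for safety. Imputed dates would still lie early within the recorded period, so item 4 matters if they are used beyond classification.
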